### 7.2.2.3 Mycophenolate Mofetil (Background Therapy)

Subjects receiving MMF prior to randomization will continue without interruption.

- Subjects must be counselled on the risk of pregnancy while taking MMF and the need for adequate contraceptive precautions (see Section 5.4, [Adequate/Effective Contraception](#)).
- Subjects on AZA or mycophenolate sodium at screening must switch to MMF at baseline (Day 1).
- For subjects who are not already taking prescribed MMF prior to randomization, the dosing of MMF will start at 500 mg BID for a total daily dose of 1 g/day for the first week, increasing to 1 g BID for a total daily dose of 2 g/day for the second and subsequent weeks (i.e., beginning on Day 8).
- Complete blood count must be performed locally at Weeks 1 and 3 in subjects not already taking MMF at screening (unscheduled visit or not).

All subjects will take MMF BID (morning and evening), before meals (i.e., on an empty stomach), with a glass of water. If a dose is missed, the subject should take the next correct dose rather than “doubling up” at the next dosing time point. A stable dose of MMF will be maintained throughout the study. Dose changes or interruptions are permitted for clearly documented safety reasons only.

- Approval by the Medical Monitor is required for subjects taking a dose other than 2 g/day MMF from randomization onwards (e.g., total daily dose of 1 or 3 g/day).
- If GI disturbance or other side-effects occur with MMF, the 1 g BID dosing may be changed to 500 mg four times daily.
- If a subject has an ANC  $<1,500/\text{mm}^3$  at any study visit, the dose of MMF should be decreased or interrupted. If a subject has an ANC  $<1,000/\text{mm}^3$  at any visit, the dose should be discontinued and only recommenced when the ANC reaches  $1,500/\text{mm}^3$ . If the subject has a dose interruption of MMF of  $>14$  days, then permanent discontinuation of MMF, therefore the study, should be considered after discussion with the Medical Monitor.
- If deemed necessary by the Investigator on account of leukopenia or other adverse effect, or if the subject weighs 50 kg or less, the dose of MMF may be decreased to a minimum of 500 mg BID.

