### 7.8.1 Prohibited Medications

The following medications cannot be taking during the study:

- IV corticosteroids within 2 weeks prior to screening (Visit 1) unless approved by the Medical Monitor
- Enteric-coated oral corticosteroids during the study are not allowed. No other use of non-enteric coated oral corticosteroids, other than administration required as per protocol, is allowed
- IV immunoglobulin treatment within 2 weeks prior to screening (Visit 1)
- Cyclophosphamide within 4 weeks prior to screening (Visit 1)
- Cholestyramine or other drugs that may interfere with enterohepatic recirculation of MMF within 4 weeks prior to screening (Visit 1)
- Initiation of new treatment or change in dosage of ARBs and/or ACE inhibitors within 4 weeks prior to randomization (Visit 2)
- CNIs (e.g., cyclosporine and tacrolimus) within 1 month of screening (Visit 1)
- Immunosuppression biologic agents (e.g., abatacept, belimumab, infliximab, adalimumab, etanercept, or rituximab) within 3 months prior to screening (Visit 1)
- Vaccines using live organisms, viral or bacterial
- MMF dose other than 2 g/day without prior discussion with the Medical Monitor
- Concomitant therapy with other immunosuppressants after randomization, other than MMF administered per protocol
- Subjects are allowed to be on AZA or mycophenolate sodium during screening but must switch to MMF at randomization
- Current or planned use of ketoconazole or rifampin
- Concomitant use of other CYP3A4/5 inhibitors and inducers should be discussed with the Medical Monitor

[Appendix 8](#) contains a summary of additional treatment and food restrictions.

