### 3 ENDPOINTS

#### 3.1 Primary Endpoint

Renal response at Week 52 will be adjudicated by the Clinical Endpoints Committee (CEC) based on the following parameters:

- UPCR of  $\leq 0.5$  mg/mg, and
- eGFR  $\geq 60$  mL/min/1.73 m^2 or no confirmed decrease from baseline in eGFR of  $>20\%$ , and
- Received no rescue medication for LN (see Protocol Section 7.8, Prohibited Therapy and Concomitant Treatment), and
- Did not receive more than 10 mg prednisone for  $\geq 3$  consecutive days or for  $\geq 7$  days in total during Weeks 44 through 52, just prior to the renal response assessment

The CEC will also take into account the following:

- Subjects who withdraw from the study prior to the Week 52 assessment and provide insufficient week 52 data to determine response will be defined as non-responders. Subjects who discontinue study drug but continue to attend study visits (as is the expectation) will have their data assessed for response.
- eGFR values eliminating a subject from complete remission should be accompanied by a treatment or disease-related treatment-emergent adverse event (TEAE) that impacts eGFR. Full details are given in Section [6.11.1](#).
- The CEC is independent and blinded from the treatment groups.

The primary endpoint estimand is the proportion of subjects showing renal response as adjudicated by the CEC in the ITT population when comparing voclosporin and placebo at Week 52. It is assessed in all randomized subjects who were recruited according to the inclusion/exclusion criteria of the protocol.

The variable is binary and indicates a response if a subject shows, at 1 year, adequate UPCR with no signs of detrimental impact on eGFR. Subjects who cannot be shown to be responders through their 1 year data (or absence thereof) are defined as non-responders.

Intercurrent events include:

- Treatment discontinuation for any reason
  - the subject remains on study, allowing the primary endpoint to be assessed at 1 year.
- Study discontinuation
  - resulting in insufficient information at 1 year to ascertain response status leading to assumed non-response.
- Rescue medication taken at any time prior to the primary assessment at 1 year
  - results in non-response. Rescue medication is adjudicated by the Clinical Endpoints Committee.
- Death at any time prior to the 1 year primary assessment
  - results in assumed non-response.

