**Table 6.1 Exposure calculation example**

Start Day	End Day	Dose (bid)	Duration
1	180	3	180 days
181	200	0	20 days
201	230	2	30 days
231	365	3	135 days

For the purposes of analysis this subject will have ‘days on treatment’ calculated as 180+30+135 = 345 days. Their mean daily dose will be:

$(180*3 + 20*0 + 30*2 + 135*3) / 365 = 2.75$  caps BID (converted to 43.45 mg per day).

Gaps between dosing records will be counted as a zero dose. For IV methylprednisolone, gaps between doses will not be taken into consideration.

For subjects who are lost to follow-up, and for whom the last dose date from the termination record is unknown, the date of the last available visit will be used as the last dose date.

Exposure to study drug will be summarized for the following:

- VCS/placebo
- MMF
- IV methylprednisolone
- Corticosteroids

Prescribed dose changes (Yes/No) at visit intervals and overall will be summarized for VCS/Placebo and for MMF.

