### 6.11.1 Primary Endpoint

The primary endpoint is the number of subjects showing renal response at 52 weeks. Renal response at Week 52 will be adjudicated by the CEC based on the following parameters:

- UPCR of  $\leq 0.5$  mg/mg, and
- eGFR  $\geq 60$  mL/min/1.73 m^2 or no confirmed decrease from baseline in eGFR of  $>20\%$ , and
- Received no rescue medication for LN, and
- Did not receive more than 10 mg prednisone for  $\geq 3$  consecutive days or for  $\geq 7$  days in total during Weeks 44 through 52, just prior to the renal response assessment

The CEC will be blind to treatment group and completely independent of Aurinia. They will also take into consideration the following:

- Subjects who withdraw from the study prior to the Week 52 assessment and thus provide insufficient Week 52 data will be defined as non-responders
- Medication listings will be reviewed by the CEC as part of the adjudication process. The CEC will have complete autonomy to adjudicate any treatment as rescue medication. However, as any dose of MMF is permitted within this protocol there is no MMF dose level that necessarily classifies it as being rescue medication. As part of this review the CEC will also adjudicate on steroid drug use beyond the protocolled taper.

- eGFR values eliminating a subject from complete remission should be accompanied by a treatment or disease-related TEAE that impacts eGFR. To this end, eGFR measures which would ordinarily result in a subject not being in remission will only be used if the first eGFR assessment occurs on a date where there is also a treatment or disease-related, eGFR associated TEAE. The following is a list of MedDRA preferred terms that are associated with eGFR decreases:
  - BLOOD CREATININE INCREASED
  - CREATININE RENAL CLEARANCE DECREASED
  - GLOMERULAR FILTRATION RATE DECREASED
  - SERUM CREATININE INCREASED
  - RENAL IMPAIRMENT
  - RENAL FAILURE
  - RENAL FAILURE ACUTE
- Confirmation of eGFR decreases from baseline require that two consecutive measures at least 3 days apart exhibit the decrease.

The null hypothesis  $H_0$  will be rejected in favor of  $H_1$  if there is evidence at the 5% significance level using a 2-sided test.

$H_0$ : There is no statistically significant difference in renal response between voclosporin and placebo at Week 52

$H_1$ : There is a statistically significant difference in renal response between voclosporin and placebo at Week 52.

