## 6.11.2 Primary Efficacy Analysis

### 6.11.2.1 Renal response at Week 52

Renal response at Week 52 will be adjudicated by the Clinical Endpoints Committee (CEC) and as such the analysis will incorporate the CEC's assessments of each subject. In order to perform their adjudication, the CEC will be provided UPCR data, eGFR data, steroid taper data, rescue and prohibited medication data and adverse event data. Full details of the adjudication process are detailed in a separate CEC Charter.

The primary efficacy analysis will be conducted on the ITT population using a logistic regression model with terms for treatment, baseline UPCR, biopsy class, MMF use at baseline and region, and renal response (Yes/No) at week 52 as the response variable (Table 14.2.1.1.2).

The results will be expressed as an odds ratio (and associated two sided- 95% CI) for voclosporin compared to placebo. Odds ratios greater than unity will mean the odds of response are greater for voclosporin than for placebo and therefore indicate a benefit of the voclosporin treatment arm. The p-value of the treatment effect will also be reported.

The following SAS program will be used for the primary efficacy analysis:

```
Proc Logistic data = data;  
Class Treatment_arm MMF_Use Biopsy_Class Region;  
Model Response = Treatment_arm MMF_Use Biopsy_Class Baseline_UPCR Region;  
Run;
```

The number of responders and non-responders at Week 52 will be summarized by treatment arm and a listing of renal responders and non-responders will also be provided.

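### SAP 6.11.1 wrongly says any MMF dose is permitted, and no ITT analysis in the visible SAP tests the result with out-of-rule MMF increases counted as non-response

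*SAP*

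**What the plan says.** **SAP.** The primary endpoint in SAP 3.1 includes the component "Received no rescue medication for LN (see Protocol Section 7.8, Prohibited Therapy and Concomitant Treatment"), and the estimand there treats rescue at any time before the one-year assessment as non-response. SAP 6.11.1 leaves the decision to the committee: "The CEC will have complete autonomy to adjudicate any treatment as rescue medication". The next sentence limits what follows from MMF dose: "However, as any dose of MMF is permitted within this protocol there is no MMF dose level that necessarily classifies it as being rescue medication".

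**Protocol.** Section 7.2.2.3 calls for a stable MMF dose throughout and adds: "Dose changes or interruptions are permitted for clearly documented safety reasons only". It also states: "Approval by the Medical Monitor is required for subjects taking a dose other than 2 g/day MMF from randomization onwards", giving 1 and 3 g/day as examples, and it sets 500 mg BID as the floor for reductions. Section 7.8.1 includes among the prohibited medications: "MMF dose other than 2 g/day without prior discussion with the Medical Monitor". That list lies inside Section 7.8, the section the rescue component refers to.

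**Data and tables.** Under SAP 6.11.2.1 "the CEC will be provided UPCR data, eGFR data, steroid taper data, rescue and prohibited medication data and adverse event data". SAP 6.9 plans a descriptive table: "Prescribed dose changes (Yes/No) at visit intervals and overall will be summarized for VCS/Placebo and for MMF". SAP 6.5 plans a summary of major protocol deviations by arm. Protocol 7.5.3 requires MMF doses, adjustments and reasons to be entered in the eCRF.

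**The concern.** MMF is active background treatment for the disease under study. If a subject is not responding and the MMF dose is raised for that reason, a later response may owe something to the increase, yet it is credited to the randomized arm unless the committee calls the increase rescue. The protocol guards against this by allowing dose changes for safety only. The SAP sentence removes that guard from the reasoning offered to the committee, because it treats every dose as allowed.

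The planned tables would show how often MMF dose changed in each arm and how many major deviations occurred. They would not show whether the treatment comparison survives if increases outside the protocol rule are counted as failures.

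**Working it through.** **1. The SAP premise against the protocol rule**

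| Point | SAP 6.11.1 | Protocol 7.2.2.3 and 7.8.1 |
|---|---|---|
| Which doses are allowed | Any | 2 g/day as standard; others need Medical Monitor approval |
| When the dose may change | Not addressed | Documented safety reasons only |
| Undiscussed dose other than 2 g/day | Covered by the general permission | Listed as prohibited |
| Is any dose level automatically rescue? | No | Not stated; 3 g/day can be approved, no ceiling is given, and 7.8 does not label any listed treatment as rescue |

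The first three rows contradict the premise. The fourth does not contradict the conclusion. SAP Section 9, which lists changes to the protocol's analyses, records no change to the MMF rule.

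**2. Does a planned analysis score these increases as non-response?**

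- *Maximum MMF dose, up to 2 g v above 2 g (SAP 6.11.2.2).* Same adjudicated endpoint, so an escalated responder stays a responder. The factor is measured after randomization and does not separate in-rule from out-of-rule increases.
- *Programmed endpoint (SAP 6.11.2.3).* Every component is derived independently except rescue, which is taken from the committee.
- *Tipping point (SAP 6.11.2.4).* Covers only outcomes assumed because data are missing.
- *Per-protocol analysis (SAP 6.1.3, 6.11.2.3).* May remove such subjects after blinded case review. It does not score them as failures and is not ITT.
- *Dose-change and deviation tables (SAP 6.9, 6.5).* Frequencies only.

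None does.

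**3. The plan's own figure**

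Inputs from Protocol 13.2: 20.0% v 34.4%, two-sided 0.05, 80% power, continuity-corrected chi-square, 162 per arm. The mean rate is 0.272 and the difference is 0.144.

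- Uncorrected: n = [1.960·√(2·0.272·0.728) + 0.842·√(0.2·0.8 + 0.344·0.656)]² / 0.144² = 148.7.
- Corrected: (148.7/4)·[1 + √(1 + 4/(148.7·0.144))]² = 162.3, which rounds up to 163.
- Power at 162 per arm is 79.9%. OR = (0.344/0.656)/(0.2/0.8) = 2.10.

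The stated 162 reproduces to within one subject. Nothing in this point disputes it.

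**4. Scale of a reclassification (illustration only)**

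The planning rates give 0.344·162 = 55.7, taken as 56, and 0.200·162 = 32.4, taken as 32. The model is the treatment-only logistic regression of SAP 6.11.2.2. With a and c the active and placebo responders, log OR = ln[a(162−c)/(c(162−a))] and SE = √(1/a + 1/(162−a) + 1/c + 1/(162−c)). For 56 v 32: ln[(56·130)/(32·106)] = 0.764, SE 0.257, z = 2.97.

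| Active v placebo responders | OR (95% CI) | Wald p | Continuity-corrected p |
|---|---|---|---|
| 56 v 32 | 2.15 (1.30–3.55) | 0.003 | 0.004 |
| 50 v 32 | 1.81 (1.09–3.02) | 0.022 | 0.030 |
| 49 v 32 | 1.76 (1.06–2.94) | 0.030 | 0.040 |
| 48 v 32 | 1.71 (1.02–2.86) | 0.040 | 0.053 |
| 47 v 32 | 1.66 (0.99–2.78) | 0.053 | 0.070 |
| 47 v 31 | 1.73 (1.03–2.90) | 0.039 | 0.051 |

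If only active-arm responders move, nine (9/162 = 5.6% of the arm) take the logistic result past 0.05, and eight do so for the corrected chi-square. One placebo responder moved as well brings the logistic p back to 0.039. The covariate-adjusted primary model cannot be run from the documents.

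**The case against.** The strongest reply is that the operative statement is correct and only its supporting clause is loose. The protocol sets no ceiling, names 3 g/day as approvable, lets prior users continue MMF without interruption, and nowhere says an out-of-rule dose is a treatment failure. The committee is blinded, independent and autonomous, and it sees prohibited-medication data. The per-protocol analysis can give a comparison without these subjects, and the maximum-dose model looks at higher MMF exposure in the ITT population. The added analysis would introduce a failure rule that the protocol does not contain, and the nine-subject scenario moves subjects in one arm only, with no documentary basis.

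Much of this stands. The conclusion about dose level should be kept, the new rule belongs in a supplementary analysis rather than the primary one, and the scenario shows scale without predicting anything: moving six active responders and none on placebo leaves p=0.022. It does not make the premise true. Nor does either of the analyses cited score the increases as non-response; excluding subjects, or adjusting for a post-randomization dose, answers a different question.

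A reader might infer that the committee is barred from treating an MMF increase as rescue, so that escalated subjects will be counted as responders. The text does not say that. It says no level *necessarily* makes MMF rescue, and it leaves the committee free to decide. The CEC Charter, which holds the adjudication details, was not available and may contain a rule.

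**Conclusion.** The point holds in limited form. The clause in SAP 6.11.1 misstates the protocol on a component of the primary endpoint, and no ITT analysis in the visible SAP text tests whether the result holds when out-of-rule MMF increases count as non-response. The second part is confined to the visible text because the list of tables in SAP Section 11 appears only as a heading and the charter was not supplied.

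The size and direction of any effect are unknown. A reader might infer that the sentence favors voclosporin. The documents do not support that: they give no frequency of increases in either arm. More escalation on placebo would make the primary analysis conservative, and more on voclosporin would flatter the drug. Whether the wrong premise would change any adjudication also cannot be known. The correction should be made because the endpoint component matters and the remedy is cheap. It is no ground for altering the primary estimand.

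**What to change.** 1. In SAP 6.11.1, replace the clause saying any dose is permitted with the protocol rule: stable dose, changes for documented safety reasons only, Medical Monitor approval for any dose other than 2 g/day. Keep the statement that no dose level is necessarily rescue.
2. Make sure the blinded data given to the committee include MMF dose changes with their recorded reasons.
3. Add one supplementary ITT analysis using the primary logistic model, with the primary estimand unchanged. Any post-randomization MMF increase above the subject's established dose without a documented safety reason counts as non-response, whether or not the Medical Monitor approved it. Exclude the Day 8 step to 2 g/day, continuation of a pre-study dose, and restoration after a safety reduction. Optionally, repeat it counting only increases that lacked Medical Monitor approval.

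The cost is one corrected clause and one extra table, or two with the optional repeat. Doses and reasons are already collected; approval status may have to be added to the listing.

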#### **3.3 Endpoints**

##### **3.3.1 Primary Endpoint**

Renal response at Week 52 will be adjudicated by the Clinical Endpoints Committee (CEC) based on the following parameters:

- UPCR of  $\leq 0.5$  mg/mg, and
- eGFR  $\geq 60$  mL/min/1.73 m^2 or no confirmed decrease from baseline in eGFR of  $>20\%$ , and
- Received no rescue medication for LN (see Section 7.8, [Prohibited Therapy and Concomitant Treatment](#)), and
- Did not receive more than 10 mg prednisone for  $\geq 3$  consecutive days or for  $\geq 7$  days in total during Weeks 44 through 52, just prior to the renal response assessment

Subjects who withdraw from the study prior to the Week 52 assessment will be defined as non-responders.

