### 6.11.2.3 Supplementary Analyses based on the Primary Endpoint

A number of supplementary analyses based around the primary endpoint will be undertaken. Different aspects of the endpoint, be they the calculation method, different data assumptions or different populations will be varied to assess the impact of each.

- Renal response at Week 52 will be derived programmatically and analyzed in an identical fashion to the primary analysis (Table 14.2.1.1.2). Using the same definition as given to the CEC and as set out in the primary endpoint section, renal response at week 52 will be derived programmatically. All components of the primary response endpoint will be independently programmed apart from the use of rescue medication. The CEC adjudication on the use of rescue medication will be incorporated into the programmed endpoint.
- The analysis described in Section 6.11.2 will be repeated for the PPS (Table 14.2.1.3).
- The analysis described in Section 6.11.2 will be repeated for each biopsy class category (Class III, Class III/V, Class IV, Class IV/V, Class V and Class VI). The combining of classes may be necessary should subject numbers in any individual class be deemed insufficient. A separate category defined as “All but Pure Class V” will be defined (Table 14.2.1.4).
- For both the adjudicated week 52 renal response (primary endpoint) and the programmed week 52 renal response (supplementary endpoint), each individual component (and some component groups) of the endpoint will be summarized by treatment group and analyzed in the same manner using a logistic regression. Analysis will be undertaken where possible, however, it is recognized that individual components may include very low numbers of subjects (either responders or non-responders). “eGFR success” is defined as an eGFR measure of  $\geq 60$  mL/min/1.73 m^2 *or* no confirmed decrease from baseline in eGFR of >20% *or* no disease-related or treatment-related AE impacting eGFR. Where data allows, the numbers of subjects achieving each of the following will be summarized (Table 14.2.1.5.1 (adjudicated) and Table 14.2.1.5.2 (programmed)):
  - UPCR  $\leq 0.5$  mg/mg

- eGFR success
- UPCr  $\leq 0.5$  mg/mg and eGFR success
- Received no rescue medication for LN
- No withdrawal prior to remission assessment

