- Did not receive more than 10 mg prednisone equivalent for  $\geq 3$  consecutive days or for  $\geq 7$  days in total during Weeks 44 through 52, just prior to the renal response assessment
- “eGFR success” will also be summarized by individual components:
  - eGFR  $\geq 60$
  - eGFR  $< 60$  with no confirmed decrease  $> 20\%$
  - eGFR  $< 60$  with confirmed decrease  $> 20\%$  but with no disease-related or treatment-related eGFR associated AE present at time of assessment.

Confirmed decrease  $> 20\%$  in eGFR is two consecutive measurements, three or more days apart by the visit where response is defined.

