### 6.13.1 Adverse Events

A treatment emergent adverse event (TEAE) is defined as:

- Any AE that has an onset on or after the first dose of study drug up to last dose + 30 days. For subjects consenting to the AURORA 2 continuation study there will be an additional constraint to the TEAE definition: events must have an onset date prior to the first dose of AURORA 2 study drug.

A treatment-related TEAE is defined as a TEAE that is assessed by the Investigator or Sponsor as being related to study drug. If a TEAE has a missing relationship to study drug it is assumed to be related to the study drug for analysis purposes.

A disease-related TEAE is defined as a TEAE that is assessed by the Investigator or Sponsor as being related to the disease under study. If a TEAE has a missing relationship to the disease under study it is assumed to be related to the disease under study for analysis purposes.

Missing severity assessments will be summarised as severe.

The following tables will be presented for AEs:

- Summary table of overall incidence, the number of events, risk difference and 95% CI (voclosporin-placebo) including the following top line summaries:
  - Any AE
  - Any TEAE
  - Any Treatment-Related TEAE
  - Any Serious TEAE
  - Any Treatment-Related Serious TEAE
  - Any TEAE Leading to Voclosporin/Placebo Discontinuation
  - Any TEAE Leading to Death
  - Treatment-Related TEAE Leading to Death
  - Disease-Related TEAE
  - Disease-Related Serious TEAE

Detailed list of AE tables is given at the end of this SAP.

In counting the number of AEs reported, a continuous event (i.e., reported more than once and which did not cease), will be counted only once for a subject; a non-continuous AE reported several times by the same subject will be counted as multiple events.

Additional tables for serious TEAEs will be provided for each of the four regions: North America, Latin America, Europe/South Africa and Asia Pacific. Similar tables will also be provided for serious TEAEs occurring between day 1 and day 84 (Up to week 12), day 85 to day 168 (Week 12 to 24) and greater than day 168 (after week 24).

All AEs will be listed and a glossary of unique verbatim terms with coding information will be provided.

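### The SAP excuses a confirmed eGFR fall unless a related adverse event is recorded, words that condition three ways, and plans no response model without it

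*SAP*

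**What the plan says.** Protocol 3.3.1, repeated in Protocol 11 and 13.7.1, sets the eGFR component as eGFR of at least 60 mL/min/1.73 m² "or no confirmed decrease from baseline in eGFR of" more than 20%. No adverse event enters the rule.

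SAP 6.11.1 repeats that component and then qualifies it: "eGFR measures which would ordinarily result in a subject not being in remission will only be used if the first eGFR assessment occurs" under a stated condition. The assessment must fall "on a date where there is also a treatment or disease-related, eGFR associated TEAE". Seven MedDRA preferred terms follow. SAP 3.1 gives a short form and refers to 6.11.1 for details.

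SAP 6.11.2.3 states the condition twice more, in the definition and breakdown of eGFR success. The definition adds a third way to succeed: "no disease-related or treatment-related AE impacting eGFR". The breakdown includes subjects below 60 with a confirmed fall of more than 20% "but with no disease-related or treatment-related eGFR associated AE present at time of assessment".

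Three other provisions bear on the trigger:

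- SAP 6.13.1 defines a TEAE as "Any AE that has an onset on or after the first dose of study drug up to last dose + 30 days".
- The same section imputes missing causality: "If a TEAE has a missing relationship to study drug it is assumed to be related to the study drug for analysis purposes". Missing relationship to the disease is handled in the same way.
- SAP 3.1 keeps off-drug subjects in the assessment: "Subjects who discontinue study drug but continue to attend study visits (as is the expectation) will have their data assessed for response".

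**The concern.** Some subjects who fail the protocol's eGFR rule pass the SAP's. Whether they pass depends partly on whether a site reported an event, how it was coded, and whether the Investigator or Sponsor judged it related. It no longer depends on the laboratory values alone.

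This would matter less if one planned analysis removed the condition. Without such an analysis, a reader who wants the treatment effect under the protocol's definition must rely on post hoc work. eGFR is a relevant component for this drug: Protocol 1.2.4.2 reports a median fall of 8-9 mL/min on voclosporin by Week 4 in Phase 2.

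The differing wordings add a smaller problem, because they can put the same subject in different categories.

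**Working it through.** **1. Does the condition change who responds?** Take a subject with Week 52 eGFR below 60, a confirmed fall of more than 20%, and no related listed event.

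| Rule | eGFR component |
|---|---|
| Protocol 3.3.1, 11, 13.7.1 | fails |
| SAP 6.11.1 | value not used, so not disqualified |
| SAP 6.11.2.3 | eGFR success |

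**2. Do the three wordings agree?**

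| Place | Event type | Timing |
|---|---|---|
| SAP 6.11.1 | related TEAE, seven listed terms | date of the first eGFR assessment |
| SAP 6.11.2.3, definition | related AE impacting eGFR | none given |
| SAP 6.11.2.3, breakdown | related eGFR-associated AE | time of assessment (which one is not stated) |

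The wording can change a classification. Suppose a subject stops study drug, keeps attending, and has a confirmed fall to below 60 with a related listed event that starts more than 30 days after the last dose. That event is not a TEAE, so 6.11.1 excuses the fall. It is still an AE, so 6.11.2.3 read literally counts a failure.

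**3. Does any response model drop the condition?**

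| Analysis | Treatment of the condition |
|---|---|
| Sensitivity and interaction models (SAP 6.11.2.2) | same endpoint, only the model differs: kept |
| Programmed response (6.11.2.3) | committee's definition: kept |
| Per-protocol and biopsy-class analyses (6.11.2.3) | repeat the primary analysis: kept |
| Tipping point (6.11.2.4) | changes only missing-data non-responders: kept |
| Week 24 response (6.11.3.4) | definitions similar to Week 52: kept |

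Partial response and the UPCR-only component contain no eGFR term, so they do not test the condition.

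**4. The plan's own figure.** Inputs from SAP 4: 20.0% versus 34.4%, 162 per arm, two-sided 0.05, continuity-corrected chi-square.

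- Corrected difference: 0.144 − 1/162 = 0.1378
- Null SE: √(2 × 0.272 × 0.728 / 162) = 0.0494
- Alternative SE: √((0.200 × 0.800 + 0.344 × 0.656) / 162) = 0.0488
- Power: Φ((0.1378 − 1.96 × 0.0494) / 0.0488) = 79.9%

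This agrees with the stated 80%. The corresponding sample-size formula gives 163 per arm against the plan's 162.

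**5. How many reclassifications would reverse the result?** Expected responders are 0.200 × 162 = 32.4 and 0.344 × 162 = 55.7, rounded to 32 and 56. The test is a pooled two-proportion z, an unadjusted approximation to the logistic model: z = (difference in proportions) / √(2p̄(1 − p̄)/162), where p̄ is the pooled proportion. For 32 versus 56, p̄ = 88/324 = 0.2716 and z = 0.1481/0.0494 = 3.00.

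| Placebo / voclosporin responders | p | p, continuity-corrected |
|---|---|---|
| 32 / 56 | 0.0027 | 0.0041 |
| 32 / 49 | 0.0292 | 0.0401 |
| 32 / 48 | 0.0393 | 0.0533 |
| 32 / 47 | 0.0523 | 0.0701 |
| 27 / 51 (5 reclassified in each arm) | 0.0018 | 0.0028 |
| 27 / 56 (5 on placebo only) | 0.0002 | 0.0004 |

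Significance is lost after 56 − 47 = 9 voclosporin-only reclassifications, or 56 − 48 = 8 with the correction. Starting from the smallest significant result with 32 placebo responders (32/48 uncorrected), one is enough. If placebo responders are also reclassified, the voclosporin count needed rises: 12 when 2 are excused on placebo (30/44, p = 0.064) and 15 when 5 are (27/41, p = 0.056).

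**The case against.** The strongest reply is that SAP 6.11.1 governs. SAP 3.1 defers to it and the programmed endpoint is tied to it, so the other two wordings affect mainly the component tables. SAP 6.13.1 defines relatedness only for TEAEs, so AE in 6.11.2.3 may be shorthand, and the off-drug example needs several uncommon conditions together. This stands as a limit: the wording problem is real but small.

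Second, several provisions make an unrecorded true decline less likely:

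- Protocol 7.6.1.1, 7.6.1.2 and 9.2.5 call for repeat tests, Medical Monitor involvement and unscheduled visits for these falls.
- Protocol 10.2.5 allows an AE for a shift to, or worsening of, a pathological value.
- Missing relatedness counts as related.
- Sites as well as the committee are blinded.

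All of this is true, but none of it forces an AE entry.

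Third, renal harm is analysed without the condition: confirmed falls of more than 30% by visit (SAP 6.11.4.2) and eGFR change from baseline (6.11.4.6). The breakdown in 6.11.2.3 also counts the excused category by arm, and excused responders cannot exceed that count. A reader can therefore bound the effect, but does not get the treatment effect on the composite with those subjects as non-responders.

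Fourth, the reversal count is one-sided. Nine is 16% of 56 voclosporin responders, with none excused on placebo, and any borderline result can be overturned by one subject. That is fair. The figures are thresholds to set against the planned counts and do not predict what will happen. The Phase 2 discontinuations for decreased GFR (6 low-dose, 1 placebo; Protocol 1.2.5) do not settle the direction either, because those falls were recorded as adverse events.

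**Conclusion.** The concern holds and should be fixed. The SAP changes the eGFR component of the primary endpoint, does not declare the change in Section 9, states the trigger in three ways, and plans no Week 52 or Week 24 response model on the protocol's rule. The endpoint is not invalid, since the condition is prespecified and applied by a blinded, independent committee. What is missing is a check.

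The size of the effect cannot be derived from the documents. The threshold of 8 to 9 assumes the design rates, an unadjusted test and reclassification on voclosporin only. Equal reclassification in both arms does not weaken the result, and reclassification on placebo only strengthens it.

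The finding that no model drops the condition covers the supplied text only. The text of SAP 6.2.13, the contents of SAP Section 11 and the CEC Charter were not available to check.

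**What to change.** Keep the adjudicated primary endpoint, and before unblinding make three changes:

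1. Prespecify a supplementary ITT logistic regression, with the primary covariates, of renal response at Week 52 and at Week 24. Count every eGFR below 60 with a confirmed fall of more than 20% as non-response, whatever the adverse-event record.
2. Use one trigger wording in SAP 6.11.1 and both places in 6.11.2.3. State which assessment date applies, and whether a TEAE or any AE is needed once a subject is more than 30 days past the last dose.
3. List the adverse-event condition in SAP Section 9 as a change from the protocol.

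The cost is some SAP wording, one extra table and one Section 9 entry, and all the data are already collected. The supplementary table may show slightly lower response rates. It would also count as non-response some of the eGFR fluctuation that Protocol 7.6.1 says does not reflect true renal dysfunction, and a table footnote should say so.
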